5.7 Statistical analyses

This trial is designed as a feasibility study and an investigation of the acceptability of the walnut intervention. The second aim is to establish preliminary efficacy for changes in fasting glucose, HbA1c and amino acid levels, for determination of sample size in a future clinical trial. Therefore, we have chosen to enroll a goal of 40 participants, including 20 in the intervention and 20 in the control groups.

Specific Aim 1: Aim 1: Determine a) feasibility for recruitment and retention into a randomized controlled trial of daily walnut supplementation, and b) acceptability and adherence to the intervention containing 28g of walnuts daily, compared with usual care in individuals with prediabetes.

Feasibility and acceptability. We will assess feasibility based on number screened and enrolled in the proposed randomized clinical trial for our goal of 40 participants. Retention over the 12-week intervention period will be assessed by number of participants who complete the final study visit at the conclusion of the intervention period. Palatability will be assessed by a 100mm visual analog scale. We will also assess acceptability of the walnut intervention, and its dose and frequency through a targeted questionnaire at the end of the intervention period. Adherence will be measured through self-report (food diaries) as well as the food frequency questionnaire administered at study completion. All questionnaires will be administered by our research assistant.

Aim 2: Determine preliminary efficacy measures for change in a) fasting glucose, HbA1c and lipid levels, b) dietary quality score and c) BCAA levels in the intervention group to inform a larger future randomized controlled trial.

Fasting glucose, HbA1c and lipids: We will obtain fasting blood samples at enrollment and at the conclusion of the study. One aliquot of serum tube of blood will be sent for fasting glucose, lipids, ApoA1 and B, and HbA1c measurement, and one aliquot of plasma will be sent for metabolomics analyses. Additional aliquots of plasma and serum will be frozen for future research purposes. We will establish preliminary efficacy for each of these measurements.

Dietary Quality: A Block food frequency questionnaire will be administered to participants at enrollment and completion of the study period. This questionnaire will use patient recall to gather frequency and serving size data for all participants. We will use the responses in this questionnaire to determine consumption of foods grouped based on likeness and culinary usage. These categories will then be transformed into 2 dietary scores: the Healthy Eating Index-2010 score, based on the Dietary Guidelines for Americans, which is a continuous score ranging from 0-100, with a score of 100 representing the optimal diet. We will also calculate the Mediterranean Diet Score, with possible values from 0-55, with 55 representing the diet most congruent with the Mediterranean diet.

BCAA, AAA and acylcarnitines: Targeted amino acid and acylcarnitine levels will be measured at baseline and at 12 weeks, post-intervention using triple quadrupole (MS/MS) and gas chromatography instruments. We will collaborate with the West Coast Metabolomic Center on the metabolomics analyses and interpretation.

Statistical Analysis: This is designed as a parallel group controlled trial, randomized on dichotomized age (<50 or \geq years) and sex (female or male). We will use Fisher's exact test and Student's t-test to compare mean baseline demographic and clinical

characteristics between the intervention and control groups. Using information from the Block food frequency questionnaire, we will construct a continuous dietary quality score using the Healthy Eating Index 2010 and Mediterranean Diet Score criteria. We will use analysis of covariance to compute the adjusted mean for our outcome variables of fasting glucose, HbA1c, HDL, LDL, total cholesterol and amino acid levels. In analysis of covariance, the baseline value of outcome variables will be used as a covariate for the computation of adjusted means between the two groups after intervention.

Expected Results: We believe that walnut supplementation will be acceptable at a dose of 28g daily. We expect to be able to recruit 40 participants within 3 months, and retain >75% for the full 12 weeks of the intervention. We expect to see a trend towards significant change in the BCAA and AAA measurements and some improvements of fasting glucose and HbA1c in the “Walnut” group compared to the “Usual care” group.

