2 SPECIFIC AIMS AND HYPOTHESES

Aim 1: Determine a) feasibility for recruitment and retention into a randomized controlled trial of daily walnut supplementation, and b) acceptability and adherence to the intervention containing 28g of walnuts daily, compared with usual care in individuals with prediabetes.

Aim 2: Determine preliminary efficacy of the walnut intervention vs. usual care on change in a) fasting glucose, HbA1c and lipid levels, b) dietary quality score and c) BCAA and AAA levels. These estimates of efficacy will inform the sample size for a larger future randomized controlled trial.

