5.4 Randomization and Blinding

Randomization: Participants will be randomly assigned to two groups of 20 participants each: “Walnuts Now” Or “Walnuts Later”. We will block our randomization by two important potential confounders: sex (female or male) and age categories (<50 or \geq 50 years). We will generate stratum-specific sequential ID numbers to randomly allocate individuals to intervention groups in blocks of four. Study staff will be blinded to the linkage between ID numbers and group assignment. Upon enrollment, each participant's stratum will be identified and the next sequential ID number from that stratum was assigned. At the end of the baseline visit, the interviewer will open a sealed, opaque envelope pre-printed with the sequential ID number revealing the intervention group assignment to the participant.

Blinding

Due to the objectives of the study, the identity of test and control treatments will be known to investigators, research staff, or patients.

This study is designed as a non-blinded trial, therefore to protect against greater than usual consumption of walnuts by the Usual Care group during the intervention period, we will offer walnut supplementation at the end of the trial to these participants. Participants in the Usual Care group will be instructed to carry out usual diet and lifestyle changes for the 12-week duration, and will receive walnut supplementation, identical in dose and duration to the intervention group, after the completion of the study.

Because of the behavioral nature of the intervention, study staff who administer the intervention and study participants will not be blinded to their intervention group assignment, however we will blind the outcomes assessments – clinical labs and amino acid analyses will be done by labs without knowledge of intervention group.

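### Randomisation is stratified by sex and age, but the planned ANCOVA adjusts only for the baseline value; if sex and age are prognostic beyond baseline, its standard errors and intervals are too wide

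*Combined protocol and SAP*

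**What the plan says.** Section 5.4 (Randomization and Blinding) sets out the stratification: "We will block our randomization by two important potential confounders: sex (female or male) and age categories". Age is split at 50 years, which gives four strata, and participants are allocated within each: staff "randomly allocate individuals to intervention groups in blocks of four".

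The statistical paragraph of section 5.7 (Statistical analyses) describes the design again, as a "parallel group controlled trial, randomized on dichotomized age" and sex. It then specifies the model: "In analysis of covariance, the baseline value of outcome variables will be used as a covariate for the computation of adjusted means". No other covariate is named there or elsewhere.

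The model is to be applied to "our outcome variables of fasting glucose, HbA1c, HDL, LDL, total cholesterol and amino acid levels". Section 2 states Aim 2 more broadly: "Determine preliminary efficacy of the walnut intervention vs. usual care on change in a) fasting glucose, HbA1c and lipid levels, b) dietary quality score", followed by BCAA and AAA levels, and says that the estimates will inform the size of a future trial. Enrolment is 40, 20 per arm, and the plan expects to "retain >75% for the full 12 weeks of the intervention".

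**The concern.** Stratified blocks make the arms alike on sex and age. If those factors predict the week-12 outcome beyond its baseline value, balancing them reduces the true sampling variance of the arm difference. A model with baseline alone cannot see that reduction: it leaves the factors' contribution in the residual, so its standard error is larger than the real spread of the estimate. The result is a conservative analysis, with intervals wider than needed in a trial of at most 40 people.

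The residual SD from this trial is also a natural input for sizing the next one. A baseline-only SD is too large for a future trial that adjusts for sex and age, and correct for one that does not. The documents do not say which is intended.

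**Working it through.** **Inputs from the documents.** Four strata and blocks of four (5.4); 40 randomised 1:1 and more than 75% retained, so about 0.75 × 40 = 30 up to 40 analysed (5.7); ANCOVA with baseline as the only covariate (5.7). The sample size of 40 is a feasibility goal with no alpha, power, effect size or SD, so there is no planning calculation to reproduce.

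**Assumed.** R² is the share of variance left after baseline that sex and age together explain. The documents give no value; 0 to 0.30 is used here.

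**Interval width, by formula.** With N analysed, the residual degrees of freedom are N − 3 (baseline only) and N − 5 (adding sex and age). Ignoring residual imbalance, adjusted width over baseline-only width is [t(0.975, N−5) / t(0.975, N−3)] × √(1 − R²). For N = 40 the t ratio is 1.0019:
- R² = 0.10: 1.0019 × √0.90 = 0.950
- R² = 0.20: 1.0019 × √0.80 = 0.896

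**Interval width, by simulation.** 40,000 trials per scenario, stratified blocks of four (the last block in a stratum may be incomplete), 40, 35 or 30 analysed at random, two strata mixes, baseline correlation 0.7. Excess width of the baseline-only 95% interval over the adjusted one:

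| R² | 40 analysed | 35 analysed | 30 analysed |
|---|---|---|---|
| 0.05 | 2% | 2% | 1% |
| 0.10 | 5% | 4–5% | 4% |
| 0.20 | 12% | 11% | 10% |
| 0.30 | 19% | 19% | 18% |

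At R² = 0 the ratio is 0.995 / 0.991 / 0.984, so needless adjustment costs roughly 0.5% / 1% / 1.7%. Break-even is at R² of about 0.01 / 0.02 / 0.03.

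**Standard error against true spread.** Let k be the share of the factors' variance contribution still in the arm difference after stratification. Model SE over true SD is then approximately 1/√(1 − R² + kR²). With equal strata k = 0.087 / 0.207 / 0.325 for 40 / 35 / 30 analysed. At R² = 0.20:
- 40 analysed: 1/√(0.80 + 0.0174) = 1.106 (simulated 1.110)
- 35 analysed: 1/√(0.80 + 0.0414) = 1.090 (simulated 1.090)
- 30 analysed: 1/√(0.80 + 0.065) = 1.075 (simulated 1.071)

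The adjusted model gives 1.003 / 1.000 / 0.996, so its standard error is right.

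**Coverage of the nominal 95% interval, baseline only.** 96.0% / 95.8% / 95.7% at R² = 0.10; about 97% / 96.5% / 96.3% at 0.20.

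**Bias.** At most 0.003 SD in every scenario.

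**Second simulation.** Programmed separately, with baseline correlation 0.6, 60% in one age group and 6,000 trials per cell. Adjusted over baseline-only width at R² = 0.20 is 0.896 with 40 analysed and 0.905 with 30; the inverses, 1.116 and 1.105, agree with the table. With 40 analysed the baseline-only model SE is 0.256 against a true 0.235.

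**Planning SD, only if the next trial also adjusts.** Baseline-only SD over adjusted SD is about 1.03, 1.06, 1.12 and 1.20 at R² = 0.05, 0.10, 0.20 and 0.30. The sample-size factor 1/(1 − R²) is 1.05, 1.11, 1.25 and 1.43. For scale, the 95% interval of a residual SD from chi-square is 0.82–1.29 times the estimate on 37 df and 0.79–1.36 on 27 df.

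**Outcome list.** Compared with Aim 2 and the measurements, the ANCOVA list leaves out:
- the two dietary quality scores, which 5.7 constructs and Aim 2b promises to compare between arms;
- triglycerides, named among the serum lipids in 5.5, while Aim 2a covers lipid levels;
- the apolipoproteins, for which 5.7 promises preliminary efficacy;
- acylcarnitines: "Targeted amino acid and acylcarnitine levels will be measured at baseline and at 12 weeks".

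The apolipoprotein is A1 in 5.5, in the laboratory paragraph of 5.6 and in 5.7, but A2 in the descriptions of both visits in 5.6.

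**The case against.** The harm is hypothetical: it needs sex and age to matter after the outcome's own baseline is in the model, and the documents offer no evidence that they do. At R² = 0.05 the gain is 1–2% of width, and below about 0.01–0.03 adjusting makes the interval slightly wider. Even at R² = 0.20 the estimate's own spread improves by only 1–3%; what changes is mainly the reported width. The plan promises adjusted means, states no confidence level or power, and attaches no decision to Aim 2. Sampling error in the SD exceeds the inflation at small R².

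All of this stands and limits the weight of the point. It does not remove it. The same excess applies to any standard error reported beside the adjusted means, and the sponsor considered both factors important enough to stratify on.

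Two further qualifications are fair. First, unbiasedness holds for complete data or dropout at random. In an open-label trial, dropout that depended on arm and on sex or age could bias a baseline-only completer analysis where those factors are prognostic, which if anything favours including them. Second, the outcome-list gaps are separate from the covariate point. The dietary-score gap is clear; triglycerides appear by name only as a measure of walnut consumption, and acylcarnitines are not in Aim 2, so their omission may be deliberate.

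**Conclusion.** The concern holds. The analysis does not reflect the stratified randomisation, and the consequence is lost reported precision, not an invalid result. The gain from adjusting becomes appreciable only if R² reaches roughly 0.10 or more, a value that is assumed and not documented. The possible cost is far smaller than the possible gain, and this justifies a recommended change to a secondary, preliminary aim. The figures assume 30 to 40 analysed, dropout at random and main effects of sex and age.

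**What to change.** In section 5.7, specify ANCOVA of the week-12 value on arm, baseline value, sex and age stratum (<50, ≥50). Report the adjusted arm difference with its 95% CI, and the residual SD both with and without sex and age, so that a future trial of either design has the right input.

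In the same edit, reconcile apolipoprotein A1 with A2 across sections 5.5, 5.6 and 5.7. Then align the ANCOVA outcome list with Aim 2 and the measurements (HEI-2010, Mediterranean Diet Score, triglycerides, apolipoproteins, acylcarnitines), or state which of these are exploratory.

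The cost is wording and two residual degrees of freedom. Both factors are already collected for randomisation, and fixing the covariates in advance also rules out choosing them after the results are seen.

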5.8 Potential problems and alternative approaches

The dose of raw, unsalted walnuts at 28g, or 1 oz, daily may not be an acceptable dose for study participants with diabetes. Based on our literature review, there have been several studies that have found a dose of 28-56g of walnuts acceptable for a similar duration. The Usual Care study arm may alter their diets to consume more walnuts during the study period given the inability to blind participants for this intervention. We plan to address this by offering walnuts after the study period to the control group, as an incentive to retain the usual care environment during the period in question. We will also be able to determine if the BCAA and AAA levels in the usual care group improve through the 12-week period as a marker of possible co-intervention.

We have considered using an active comparator to walnuts, however with the possibility of confounding biological activity for other whole food supplements, we elected not to include one for this pilot study given our goals of feasibility, acceptability, adherence and preliminary efficacy of a walnut intervention. Instead, we feel that providing walnuts for all of the trial participants, using the approach that the intervention group will receive walnuts during the main study period, and the control group will continue with usual care during the intervention period, but then receive walnuts later as a “walnuts now” vs. “walnuts later” approach will help to control for confounding. If we are successful in our primary outcomes, we will consider an active comparator for our larger randomized controlled trial.

5.9 Study limitations

Generalizability: We aim to recruit subjects who self-identify as overweight or obese, with prediabetes, and will assess their laboratory criteria for prediabetes at the first visit. Our study design is a convenience sample of volunteers who are motivated to participate in a clinical study, all factors which limit generalizability. Our study population should be representative for our target population of overweight or obese adults with prediabetes between the ages of 18 and 65. We will be unable to accommodate participants who do not speak English due to difficulties in finding qualified study personnel who speak other languages.

6 PROTECTION OF HUMAN SUBJECTS

6.1 Risks to the Subjects

6.1.a Human Subject Involvement and Characteristics: We will be enrolling approximately 40 volunteers who are overweight or obese and who fulfill criteria for prediabetes.

Eligibility criteria are listed below:

Inclusion Criteria

1. Male or female between 18-65 years of age at baseline living in the San Francisco Bay area.
2. $BMI > 25 \text{ m/kg}^2$ (or $> 23 \text{ m/kg}^2$ for individuals of Asian or South Asian ethnicity)
3. Documentation of prediabetes diagnosis as evidenced by the following criteria:
 - a. A fasting glucose 100-125 mg/dL, or a HbA1c measurement of 5.7-6.4%, OR a diagnosis of "prediabetes" or "impaired fasting glucose" in the past 6 months, identified through an electronic medical record query from patients at UCSF and through outside recruitment in the surrounding community
 - b. We will confirm eligibility of potential participants by repeating fasting capillary blood glucose measurements at the baseline visit to ensure that they have prediabetes
4. Written informed consent and ability for subject to comply with the requirements of the study.

Exclusion Criteria

1. Pregnant or breastfeeding women at enrollment.
2. Presence of a condition or abnormality that in the opinion of the Investigator would compromise the safety of the patient or the quality of the data, such as diverticulosis or diverticulitis.
3. Tree or peanut allergies
4. Unwilling to consume a daily walnut supplement.
5. Diagnosis of diabetes
6. On glucose lowering medications
7. Dietician-managed dietary intake, or personal or medical dietary restrictions that do not allow consumption of walnuts
8. Malabsorptive conditions including intestinal bypass surgery, pancreatitis, inflammatory bowel disease

All subjects should be maintained on the same medications throughout the entire study period, as medically feasible, with no introduction of new glucose-lowering therapies.

6.1.b Sources of Materials: All personal, medical, and biochemical, data collected during the studies are for research purposes only, although test results that come from

certified laboratories can be provided to patients or their physicians upon request with the subject's permission.

6.1.c Potential Risks:

Capillary blood glucose measurement: The baseline visit will require fingerstick collection of one drop of blood for determination of eligibility. This may result in pain or discomfort. We do not anticipate other problems from this procedure in healthy adults.

Phlebotomy and venipuncture: The baseline visit and study conclusion visit 3-month visit will require approximately 35-45 ml of venous blood collection. We do not anticipate any problems with anemia with a total of 45 ml of blood collection in our study of healthy volunteers. Venipuncture may result in a hematoma, which can be painful but carries no significant risks. Infections rarely occur from such brief interventions.

Walnut supplementation: There is minimal risk associated with participation in the walnut intervention. There is the possibility of an allergic reaction to the walnut supplement. We will actively exclude any participants with a known tree nut or peanut allergy from enrollment in the study. There is the small possibility that an as-yet, unknown, allergy to walnuts will occur during the course of the study. In the event of signs or symptoms of allergy, the walnut intervention will be discontinued. Participants will be educated on signs and symptoms of a walnut allergy at the baseline visit. In order to protect the integrity and freshness of the walnuts, they will be kept in cold storage at the study site, and participants will be instructed to keep them in cold storage in their private homes before use.

6.2 Adequacy of Protection Against Risks

6.2.a Recruitment and Informed Consent: Recruitment will be accomplished primarily through a medical records query, and through flyers at Parnassus and Mount Zion UCSF campuses. At the beginning of the baseline visit, a member of the research staff will review the consent form in detail with the patient and answer all questions before inviting the patient to sign the consent form. A photocopy of the signed consent form with the Experimental Subjects' Bill of Rights is given to the patient. The protocols are reviewed by the Institutional Committee on Human Research, University of California, San Francisco and University of California, San Diego. All subjects will be reimbursed for the time and possible inconvenience associated with participation in the studies.

6.2.b Protection Against Risk: The specific measures to minimize each risk are described in the relevant sections above, as well as the Data Safety and Monitoring Plan that is outlined in a subsequent section. In addition, there will be continuous safety surveillance with emphasis on the potential side effects of each procedure, as detailed above. Participation in the study will be discontinued if the subject fails to adhere to the study requirements in a way that may cause harm to him or herself or seriously interfere with the validity of the study results; or the investigator determines that further participation would be detrimental to the subject's health or well being.

Subjects who are injured as a result of being in this study will have treatment available.

The costs of such treatments may be covered by the University of California depending on a number of factors.

Participation in research may involve a loss of privacy. Research records will be kept confidential to the extent permitted by law. Subjects will be identified by a code, and personal information from records will not be released without written permission. Subjects will not be personally identified in any publication about this study.

6.3 Potential Benefits of the Proposed Research to the Subjects and Others

There is no guaranteed benefit to the subjects who participate in this study. To the extent allowable, results of laboratory tests are made available to subjects and/or their primary care providers that might prove useful in their clinical management or prevention of future disease.

